7.3. Exclusion Criteria

The presence of any of the following will exclude a subject from enrollment:

1. Subject has Down syndrome.
2. Subject has French-American-British classification (FAB) type M3 leukemia (acute promyelocytic leukemia) or identification of t(15;17).
3. Subject has isolated CNS involvement or extramedullary relapse. (Subjects with combined CNS/marrow relapse may be enrolled).
4. Subject has had prior treatment with cytotoxic chemotherapy within 2 weeks of the first dose of lenalidomide with the exception of hydroxyurea (allowed prior to the first dose of lenalidomide and through Day 14 of Cycle 1) and intrathecal (IT) cytarabine will be administered within 2 weeks prior to administration of lenalidomide.
5. Subject has had prior treatment with biologic antineoplastic agents less than 7 days before the first dose of lenalidomide. For agents that have known AEs occurring beyond 7 days after administration (ie, monoclonal antibodies), this period must be extended beyond the time during which acute AEs are known to occur.
6. Subject has had prior treatment with lenalidomide.
7. Subject is pregnant or lactating.
8. Subject has an uncontrolled systemic fungal, bacterial, or viral infection (defined as ongoing signs/symptoms related to the infection without improvement despite appropriate antibiotics, antiviral therapy, and/or other treatment).
9. Subject has known Human Immunodeficiency Virus (HIV) positivity (subjects who are receiving antiretroviral therapy for HIV disease).
10. Subject has a prior history of malignancies other than AML unless the subject has been free of the disease for ≥ 5 years from first dose of lenalidomide.
11. The presence of any of the following will exclude a subject from enrollment:
 - Subject has any significant medical condition, laboratory abnormality, or psychiatric illness that would prevent the subject from participating in the study.

- Subject has any condition including the presence of laboratory abnormalities, which places the subject at unacceptable risk if he/she were to participate in the study.
 - Subject has any condition that confounds the ability to interpret data from the study.
12. Subject has cardiac disorders (Common Terminology Criteria for Adverse Events [CTCAE] version 4.03 Grade 3 or 4).
 13. Subject has a history of well-documented prior veno-occlusive disease (VOD).
 14. Subject has any other organ dysfunction (CTCAE version 4.03 Grade 4) that will interfere with the administration of the therapy according to this protocol.

7.4. Inclusion and Exclusion Criteria for OEP

Refer to [Appendix L](#) – Optional Extension Phase.

Note: *True abstinence is acceptable when this is in line with the preferred and usual lifestyle of the subject. [Periodic abstinence (eg, calendar, ovulation, symptothermal, post-ovulation methods) and withdrawal are not acceptable methods of contraception].

8. DESCRIPTION OF STUDY TREATMENTS

8.1. Description of Investigational Product(s)

Investigational product will be provided as capsule formulation and as active pharmaceutical ingredient (API) in vials for constitution to oral suspension.

Celgene Corporation will supply lenalidomide 2.5 mg, 5 mg, 10 mg, 15 mg, 20 mg and 25 mg capsules as hard gelatin capsules for oral administration. The 2.5 mg dose is contained in a size 4 hard gelatin capsule. The 5 mg dose is contained in a size 2 hard gelatin capsule. The 10 mg, 15 mg, 20 mg and 25 mg doses are contained in a size 0 hard gelatin capsule. Lenalidomide capsules should be swallowed whole and should not be broken, chewed or opened. Each dosage will be provided in 21 count bottles.

Celgene Corporation will supply lenalidomide API in individual sealed vials for constitution to oral suspension. Each vial contains 80 mg of lenalidomide with no inactive ingredients. The lenalidomide powder in each vial is constituted with 8 ml of suspending agent to create a lenalidomide suspension with a final concentration of 10 mg/ml. This suspension is intended for oral administration only.

Females of child bearing potential (FCBP) should not handle or administer lenalidomide unless they are wearing gloves. All subjects should not extensively handle the lenalidomide capsules or oral suspension. The lenalidomide capsules should not be broken, chewed, or opened and should be maintained in the packaging until ingestion. Refer to the subject diary and the manual on preparation, administration, and handling of the lenalidomide oral suspension for specific details.

If a subject is receiving lenalidomide oral suspension, a home healthcare company can be available to assist with the preparation and administration of the oral suspension at the subject's home. The home trial support agent that may visit the subject's home would be a licensed nurse. Refer to the manual on preparation, administration, and handling of the lenalidomide oral suspension for specific details.

In investigational studies, lenalidomide will be dispensed through a qualified healthcare professional (including but not limited to nurses, pharmacists and physicians). These healthcare professionals will be trained by Celgene in requirements specific to counseling of subjects. Once trained, these healthcare staff will counsel subjects prior to lenalidomide being dispensed to ensure that the subject has complied with all requirements (including use of birth control and pregnancy testing for FCBP) and that the subject understands the risks associated with lenalidomide. This step will be documented with a completed Education and Counseling Guidance Document and no lenalidomide will be dispensed until this step occurs. Counseling includes verification with the subject that required pregnancy testing was performed and results were negative.

A Lenalidomide Information Sheet will be supplied each time lenalidomide is dispensed.

8.2. Treatment Administration and Schedule

Lenalidomide will be administered either in capsules containing 2.5 mg, 5 mg, 10 mg, 15 mg, 20 mg or 25 mg or as an oral suspension (10 mg/mL). The oral suspension is available for use in

subjects who are unable to swallow the capsules or at the discretion of the investigator. The starting dose of lenalidomide will be 2 mg/kg/day with a maximum dose of 70 mg/day. Lenalidomide will be administered orally once daily for the first 21 days of every 28-day cycle. Daily dosage should be administered using the combinations that yield the least amount of capsules. However, if a subject is unable to swallow big capsules, varying, appropriate strength combinations may be considered during medication assignment using the IWRS. The prescribed dose should be the closest dose that can be given to the calculated dose based on the strengths of lenalidomide available. If the calculated dose falls between two integers, the dose calculated should be rounded up or down to the nearest whole number. The actual dose to be administered can be determined after rounding the calculated dose. For dose reductions, the dose calculated should be to the nearest whole number. For a dosing table with guidelines reflecting this approach for the lenalidomide capsules, refer to [Appendix B](#).

Refer to [Appendix C](#) for dosing guidelines for the lenalidomide oral suspension.

After completion of 12 cycles of study treatment, if deemed necessary or useful by the Investigator and with approval of the Sponsor, subjects who demonstrate clinical benefit as per the Investigator from lenalidomide may continue to receive oral lenalidomide (either capsules or oral suspension) in an OEP until they meet the criteria for study discontinuation (see [Section 12](#)).

Dose interruptions/reductions will be permitted for episodes of myelosuppression, non-hematologic toxicities, and AEs. For additional details see [Section 8.2.1](#).

In the event of specific protocol-defined toxicity, no more than 2 dose reductions will be allowed to doses of 1.4 mg/kg/day (not exceeding 50 mg/day) and 1 mg/kg/day (not exceeding 35 mg/day) during the study. The dose will not be re-escalated once it has been reduced ([Table 6](#)). Subjects who do not tolerate the minimum dose level of 1 mg/kg/day (not exceeding 35 mg/day) will be discontinued from the study.

As per routine standard of care, intrathecal cytarabine (age-based dosing) will be administered prior to Cycle 1 in all subjects at the time of screening through lumbar puncture ([Table 5](#)). Intrathecal cytarabine will be administered within 2 weeks prior to administration of lenalidomide:

- For subjects without CNS involvement, subsequent intrathecal cytarabine may be administered at the discretion of the treating physician.
- For subjects with CNS involvement at screening, intrathecal cytarabine will be administered twice weekly x 4 doses and until CSF is clear on 2 consecutive evaluations for up to 6 total doses.
 - Subjects whose CSF was cleared may receive subsequent intrathecal cytarabine doses at the discretion of the treating physician.
 - Subjects who have persistent CNS disease despite 6 doses of intrathecal cytarabine will be off study treatment.

Table 5: Age-based Cytarabine Dosing

Age (years)	Dose
0 – 0.99	20 mg
1 – 1.99	30 mg
2 – 2.99	50 mg
≥ 3	70 mg

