6.17. IP Dispensing

Lenalidomide should be dispensed on Day 1 of every cycle including the OEP. Only enough lenalidomide for 1 cycle of therapy will be dispensed with each cycle of therapy. The first dose of lenalidomide will be administered at the study center after the completion of all clinical procedures required for Cycle 1 Day 1 with the exception of the collection of PK sampling. When multiple capsules are required to make up the accurate daily dosage, detailed instructions will be provided to the subject to ensure accurate dosages are taken ([Appendix B](#)).

Refer to [Appendix C](#) for dosing guidelines for the lenalidomide oral suspension.

Detailed instructions on preparation, administration, and handling of the lenalidomide oral suspension will be provided in a separate manual.

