8.2.1. Dose Reductions/Interruptions

Dose reduction guidelines are as follows:

- Two dose reductions will be allowed (Table 6) in the event of specific protocol-defined toxicity. If treatment is interrupted for toxicity as described below, lenalidomide will be resumed at dose level -1 once the toxicity has resolved to ≤ Grade 1. If toxicity recurs, lenalidomide will be interrupted and upon resolution, the subject will resume at dose level -2.
- The dose will not be re-escalated if the lower dose is tolerated.
- Subjects who do not tolerate 1 mg/kg/day (dose level -2) will discontinue lenalidomide administration.

Table 6: Dose Reductions of Lenalidomide

Dose Level	Dose
Starting dose	2.0 mg/kg/day (maximum dose of 70 mg/day for subjects ≥ 35 kg)
Dose Level -1	1.4 mg/kg/day (not exceeding 50 mg/day for subjects initially dosed at 70 mg/day)
Dose Level -2	1.0 mg/kg/day (not exceeding 35 mg/day for subjects initially dosed at 70 mg/day)

Definition of Toxicity Requiring Treatment Interruption and/or Dose De-escalation

Lenalidomide dosing will be interrupted for any of the following toxicities at least possibly attributed to lenalidomide:

- Any Grade 4 non-hematological toxicity *with the specific exclusion* of fever or infection.
- Any Grade 3 non-hematological toxicity *with the specific exclusion* of:
 - Grade 3 nausea and vomiting controlled by antiemetics.

- Grade 3 fever or infection.
- Grade 3 hypophosphatemia, hypokalemia, hypocalcemia or hypomagnesemia responsive to oral supplementation.
- Grade 3 TLS: With close monitoring per the [REDACTED] TLS monitoring guidelines ([Appendix M](#) Tumor Lysis Syndrome), lenalidomide dose may be continued uninterrupted provided continued treatment does not pose a safety concern in the presence of TLS event. If interrupted, lenalidomide treatment may be restarted at the same dose level after TLS is under control at the discretion of the Investigator.

NOTE: For purposes of grading AST and ALT adverse events in this study, the ULN for AST is 50 U/L and the ULN for ALT is 45 U/L.

Lenalidomide will be held for any subject experiencing hemorrhagic or bullous skin rash until a specific evaluation to exclude toxic epidermal necrolysis and/or Stevens-Johnson syndrome has been performed. Any subject with evidence of TEN or Stevens-Johnson syndrome will not be retreated with lenalidomide.

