8.2.2. Overdose

Overdose, as defined for this protocol, refers to lenalidomide dosing. On a per dose basis, an overdose is defined as the following amount over the protocol-specified dose of lenalidomide assigned to a given subject, regardless of any associated AEs or sequelae.

- >10% over the protocol-specified dose.

On a schedule or frequency basis, an overdose is defined as anything more frequent than the protocol-required schedule or frequency.

Complete data about drug administration, including any overdose, regardless of whether the overdose was accidental or intentional, should be reported in the CRF. See Section 11 for the reporting of AEs associated with overdose.

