Appendix B: Lenalidomide Dosing Table – Capsule

Lenalidomide* Dosing Table – Capsule							
Calculated Dose (mg/day)**	Actual Dose Administered (mg/day)	Number of Capsule Strength					
		2.5 mg	5 mg	10 mg	15 mg	20 mg	25 mg
15	15				1		
16	15				1		
17	17.5	1			1		
18	17.5	1			1		
19	20					1	
20	20					1	
21	20					1	
22	20					1	
23	22.5	1				1	
24	25						1
25	25						1
26	25						1
27	25						1
28	27.5	1					1
29	30		1				1
30	30		1				1
31	30		1				1
32	30		1				1
33	35			1			1
34	35			1			1
35	35			1			1
36	35			1			1
37	35			1			1
38	40					2	
39	40					2	
40	40					2	
41	40					2	
42	40					2	
43	45					1	1
44	45					1	1
45	45					1	1
46	45					1	1
47	45					1	1
48	50						2
49	50						2

Lenalidomide* Dosing Table – Capsule							
Calculated Dose (mg/day)**	Actual Dose Administered (mg/day)	Number of Capsule Strength					
		2.5 mg	5 mg	10 mg	15 mg	20 mg	25 mg
50	50						2
51	50						2
52	50						2
53	52.5	1					2
54	55		1				2
55	55		1				2
56	55		1				2
57	60					3	
58	60					3	
59	60					3	
60	60					3	
61	60					3	
62	60					3	
63	65				1		2
64	65				1		2
65	65				1		2
66	65				1		2
67	65				1		2
68	70					1	2
69	70					1	2
70	70					1	2

* Using CC-5013 strengths: 2.5 mg (Size 4), 5 mg (Size 2), 10 mg (Size 0), 15 mg (Size 0), 20 mg (Size 0) and 25 mg (Size 0).

** If the calculated dose falls between two integers, the dose calculated should be rounded up or down to the nearest whole number. The actual dose to be administered can be determined after rounding the calculated dose.

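### Appendix B, row 57 mg: the capsule table gives 60 mg, although 55 mg is closer and takes the same three capsules

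*Protocol*

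**What the plan says.** Section 8.2 lists the strengths: "Lenalidomide will be administered either in capsules containing 2.5 mg, 5 mg, 10 mg, 15 mg, 20 mg or 25 mg". It then gives two instructions for building a capsule dose. The first concerns capsule count: "Daily dosage should be administered using the combinations that yield the least amount of capsules". The second concerns accuracy: "The prescribed dose should be the closest dose that can be given to the calculated dose based on the strengths of lenalidomide available". The section does not rank them. It continues "For a dosing table with guidelines reflecting this approach for the lenalidomide capsules, refer to" Appendix B, so the table is meant to follow from these two instructions.

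Appendix B has one row per whole milligram from 15 to 70 mg, 56 rows in all. Its footnote has the calculated dose rounded to a whole number first, and then: "The actual dose to be administered can be determined after rounding the calculated dose". Rows 54, 55 and 56 give 55 mg as 2 x 25 mg + 1 x 5 mg. Rows 57 to 62 give 60 mg as 3 x 20 mg.

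Section 6.17 also cites Appendix B: "When multiple capsules are required to make up the accurate daily dosage, detailed instructions will be provided to the subject to ensure accurate dosages".

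**The concern.** At 57 mg the table moves up to 60 mg one row too early. The 55 mg combination of the row above is 1 mg closer to 57 mg and takes the same number of capsules. Closeness therefore favours 55 mg, and capsule count is a tie.

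Sites take the capsule dose from this table, so a child whose calculated dose rounds to 57 mg would be dispensed 60 mg. What is at stake is the accuracy of one row of a paediatric dosing table. No endpoint, stopping rule or analysis depends on it.

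**Working it through.** **Inputs.** Strengths 2.5, 5, 10, 15, 20 and 25 mg (Section 8.2); the 56 listed doses (Appendix B); starting dose 2 mg/kg and the reduced levels (Section 8.2.1, Table 6).

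**Step 1: the row as listed.** 3 x 20 = 60 mg, so the dose column and the capsule column agree with each other. A shifted column is unlikely.

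**Step 2: candidate doses for 57 mg.** Gap = |dose - 57|; deviation = dose/57 - 1; the last column divides by 28.5 kg (57/2).

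| Dose | Combination | Capsules | Gap | Deviation | mg/kg/day at 28.5 kg |
|---|---|---|---|---|---|
| 60 mg (listed) | 3 x 20 | 3 | 3 mg | +5.3% | 2.11 |
| 55 mg | 2 x 25 + 5 | 3 | 2 mg | -3.5% | 1.93 |
| 57.5 mg | 2 x 25 + 5 + 2.5 | 4 | 0.5 mg | +0.9% | 2.02 |

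Three is the minimum capsule count for both 55 and 60 mg, and four is the minimum for 57.5 mg.

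**Step 3: does either order of the two instructions give 60 mg?** Closest dose first gives 57.5 mg. Fewest capsules within a tolerance, then closest, gives 55 mg at each tolerance tried (2, 2.25, 2.5, 3, 3.5, 4 and 5 mg). Neither gives 60 mg.

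**Step 4: is this a convention of the table?** For every row, the listed dose was compared with the closest dose obtainable with no more capsules.

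- Gap between calculated and listed dose: 0 mg in 12 rows, 0.5 mg in 5, 1 mg in 22, 2 mg in 16 and 3 mg in one. The last is row 57.
- In 17 rows the listed dose is not the closest achievable: 22, 27, 32, 33, 37, 38, 42, 43, 47, 48, 52, 57, 58, 62, 63, 67 and 68. In 16 of them every closer dose costs an extra capsule. Row 57 is the exception.
- Rows 22, 27, 32, 37, 42, 47, 52, 62 and 67 all round down by 2 mg. Row 57, in the same position in the sequence, rounds up by 3 mg.

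**Step 5: proportional context.** Row 57 is not the largest relative deviation. Row 22 gives 20 mg (-9.1%), row 27 gives 25 mg (-7.4%) and row 33 gives 35 mg (+6.1%); in each, a closer dose needs a second or third capsule. Row 16 gives 15 mg (-6.2%), which is already the closest dose.

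**Step 6: who is affected.** At 2 mg/kg, a calculated dose that rounds to 57 mg means 56.5/2 to 57.5/2 = 28.25 to 28.75 kg. Before rounding, 55 mg is 1.5 to 2.5 mg away across this band and 60 mg is 3.5 to 2.5 mg away. So 55 mg is never the further of the two, and they tie only at 28.75 kg. At 1.4 mg/kg the row would need 56.5/1.4 to 57.5/1.4 = 40.4 to 41.1 kg. A child of that weight starts at 70 mg, and Table 6 limits dose level -1 to "1.4 mg/kg/day (not exceeding 50 mg/day for subjects initially dosed at 70 mg/day"). At 1.0 mg/kg it would need 56.5 to 57.5 kg, where the limit is 35 mg. The row therefore arises at the starting dose only.

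**Step 7: amount of drug.** Over 21 days, 60 x 21 = 1,260 mg and 55 x 21 = 1,155 mg, a difference of 105 mg per course.

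**The case against.** **The row does not break the capsule-count instruction.** Three capsules is the fewest for 60 mg, so 3 x 20 mg complies with it. A reader might infer that row 57 violates both instructions. The documents do not support that. They support only that neither instruction gives a reason to prefer 60 mg to 55 mg. This part of the objection stands.

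**Measured by closeness alone, row 57 is one of 17.** The table plainly gives up closeness to save capsules, and the test that singles out row 57 (closer dose, no extra capsule) is not written in the protocol. That is true, but the test assumes no ranking of the two instructions. A choice that is worse on one and no better on the other cannot follow from them in either order.

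**The proposed 55 mg is not the closest dose either.** That is 57.5 mg. This stands, and the choice depends on a ranking that Section 8.2 does not state. Most of the table accepts a gap of up to 2 mg to avoid a capsule, which points to 55 mg.

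**A uniform strength may be simpler.** No such preference is stated, and rows 54 to 56 and 63 to 67 mix strengths. The one stated exception, for subjects who cannot swallow big capsules, does not help: by Section 8.1 the 20 and 25 mg capsules are size 0 and the 5 mg capsule is size 2. Thus 60 mg needs three size 0 capsules and 55 mg needs two.

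**The effect is negligible.** It concerns a 0.5 kg band, capsule users only (Appendix C gives 58 mg as suspension), in a trial of at most 47 subjects. Section 6.12 adjusts the dose only for weight changes of 10% or more. This stands and sets the severity.

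**Conclusion.** The point holds as a minor arithmetic slip in one row. Row 57 gives 60 mg (+3 mg, +5.3%) where 55 mg (-2 mg, -3.5%) is closer with the same three capsules, and it is the only row of 56 with this property.

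Two stronger inferences are not supported. The row is not an overdose: Section 8.2.2 sets the limit at more than "10% over the protocol-specified dose", and 5.3% is well below it. Nor is it the worst row in relative terms, although it has the largest gap in milligrams.

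The conclusion rests on the strengths listed in Section 8.2 and on reading Appendix B as the application of that section, which the section itself says. The choice of 55 rather than 57.5 mg also assumes that capsule count outweighs a gap of 2 mg, as it does in most of the table.

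**What to change.** Change Appendix B row 57 to 55 mg, given as 1 x 5 mg + 2 x 25 mg, the combination already in rows 54 to 56. The largest gap in the table then falls from 3 mg to 2 mg. If the sponsor ranks closeness above capsule count, use 57.5 mg (2 x 25 mg + 5 mg + 2.5 mg) instead; in that case the other 16 rows that give up closeness to save a capsule would need the same review.

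Cost: one table row, and the same row wherever the table is built into the dispensing system. With 55 mg the capsule count stays at three; with 57.5 mg it rises to four.

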8.2.1. Dose Reductions/Interruptions

Dose reduction guidelines are as follows:

- Two dose reductions will be allowed (Table 6) in the event of specific protocol-defined toxicity. If treatment is interrupted for toxicity as described below, lenalidomide will be resumed at dose level -1 once the toxicity has resolved to ≤ Grade 1. If toxicity recurs, lenalidomide will be interrupted and upon resolution, the subject will resume at dose level -2.
- The dose will not be re-escalated if the lower dose is tolerated.
- Subjects who do not tolerate 1 mg/kg/day (dose level -2) will discontinue lenalidomide administration.

Table 6: Dose Reductions of Lenalidomide

Dose Level	Dose
Starting dose	2.0 mg/kg/day (maximum dose of 70 mg/day for subjects ≥ 35 kg)
Dose Level -1	1.4 mg/kg/day (not exceeding 50 mg/day for subjects initially dosed at 70 mg/day)
Dose Level -2	1.0 mg/kg/day (not exceeding 35 mg/day for subjects initially dosed at 70 mg/day)

Definition of Toxicity Requiring Treatment Interruption and/or Dose De-escalation

Lenalidomide dosing will be interrupted for any of the following toxicities at least possibly attributed to lenalidomide:

- Any Grade 4 non-hematological toxicity *with the specific exclusion* of fever or infection.
- Any Grade 3 non-hematological toxicity *with the specific exclusion* of:
 - Grade 3 nausea and vomiting controlled by antiemetics.

- Grade 3 fever or infection.
- Grade 3 hypophosphatemia, hypokalemia, hypocalcemia or hypomagnesemia responsive to oral supplementation.
- Grade 3 TLS: With close monitoring per the [REDACTED] TLS monitoring guidelines ([Appendix M](#) Tumor Lysis Syndrome), lenalidomide dose may be continued uninterrupted provided continued treatment does not pose a safety concern in the presence of TLS event. If interrupted, lenalidomide treatment may be restarted at the same dose level after TLS is under control at the discretion of the Investigator.

NOTE: For purposes of grading AST and ALT adverse events in this study, the ULN for AST is 50 U/L and the ULN for ALT is 45 U/L.

Lenalidomide will be held for any subject experiencing hemorrhagic or bullous skin rash until a specific evaluation to exclude toxic epidermal necrolysis and/or Stevens-Johnson syndrome has been performed. Any subject with evidence of TEN or Stevens-Johnson syndrome will not be retreated with lenalidomide.

Grade 3 ALT/AST values that return to levels that meet initial eligibility criteria within 7 days of IP interruption do not require a dose reduction. These subjects may resume treatment at the original dose level. If the toxicity recurs, then dose de-escalation is indicated.

Day 1 of Cycle 2 and beyond may be delayed up to 14 days from the end of the prior cycle in order for subjects to recover from toxicity. If a study interruption has lasted for more than 14 days, the Investigator should contact the Medical Monitor to discuss whether the subject should be continued on the study.

Special Instructions for Myelosuppression:

Due to the underlying marrow infiltrating malignancy, myelosuppression is universal and expected in patients with AML. Therefore, myelosuppression (anemia, neutropenia, and thrombocytopenia) will not require dose reduction or interruption *except* in the case of neutropenia or thrombocytopenia due to prolonged bone marrow aplasia at the end of a treatment cycle in subjects who have achieved remission.

- For subjects who have achieved remission:
 - Prolonged bone marrow aplasia is defined as lack of peripheral blood count recovery to $ANC \geq 500/mm^3$ and platelets $\geq 50,000/mL$ without transfusion for 7 days in the absence of leukemia (bone marrow biopsy demonstrate hypocellularity without evidence of leukemia) at Day 43 of a cycle (ie, failure to start the next cycle within 14 days).
 - The lenalidomide dose will be interrupted and the start of the next cycle will be delayed until count recovery.
 - Prolonged delay (ie, failure to start the next cycle within 14 days) for subjects in remission will require dose de-escalation.
 - If the peripheral blood counts recover within 14 days, the subject will proceed to the next cycle without dose reduction.

- If the peripheral blood counts do not recover within 14 days, repeat bone marrow evaluation including bone marrow biopsy every 7-14 days to assess cellularity and to evaluate for relapse/persistent leukemia.
- For subjects who have not achieved remission:
 - In general, subjects who have not achieved remission and have evidence of residual leukemia will proceed to the next cycle as scheduled regardless of count recovery.
- For subjects with residual leukemia:
 - If residual leukemia is demonstrated and the subject previously had achieved CR/CRi, the subject will be discontinued from the study.
 - If residual leukemia is demonstrated, which is stable from prior assessments (ie, subject with previous PR/treatment failure), the subject will proceed to the next cycle of lenalidomide as scheduled without delay and without regard to peripheral blood counts. Lenalidomide dose will NOT be decreased.

Special Instructions for Management of Graft Versus Host Disease (GVHD):

Post-HSCT subjects will be monitored closely for development of GVHD of the skin, liver, or gut, see [Appendix K](#) for grading criteria.

- Subjects with Grade 1 or 2 GVHD (any site, biopsy proven or probable, ie, requires systemic steroid treatment) will be managed at the discretion of the local bone marrow transplant (BMT) physician and lenalidomide will be held.
 - If the acute GVHD resolves within 14 days and the subject is being treated with no more than topical therapies and/or up to 0.5 mg/kg/day corticosteroids (prednisone equivalents), lenalidomide will be restarted at the same prior dose.
 - After 14 days, subjects requiring more than 0.5 mg/kg/day corticosteroids or other systemic therapy (ie, not including topical therapies) to manage the acute GVHD will be discontinued from the study.
- Subjects with Grade 3 or 4 GVHD (any site, suspected or biopsy proven) will have lenalidomide discontinued permanently and will be managed at the discretion of the local HSCT physician. These subjects will be discontinued from the study.

Guidelines for Renal Insufficiency

- Lenalidomide is primarily excreted unchanged by the kidney; therefore, study treatment will be held for subjects who experience CLcr < 70 mL/min (confirmed by repeat creatinine measurement within 3 days). If CLcr returns to levels that meet initial eligibility criteria (> 70 mL/min) within 7 days of IP interruption, the subject may resume treatment at a full dose. However, if the subject improves within 14 days, a dose reduction by 1 dose level of study treatment will be considered at the discretion of the Investigator, and after careful consideration of the subject's renal impairment etiology and the subject's tolerability to lenalidomide. If toxicity does not resolve to eligibility by 14 days of dose interruption, then the subject will be off study treatment.

Dose Discontinuation:

- Subjects experiencing a thromboembolic event unrelated to a central line will be discontinued from lenalidomide treatment.
- As described above, under dose interruption, any subject with evidence of TEN or Stevens-Johnson syndrome will not be retreated with lenalidomide.
- Subjects who do not tolerate 1 mg/kg/day will discontinue lenalidomide treatment.
- Subjects with non-hematologic toxicities that do not resolve to less than or equal to Grade 1 or baseline levels within 14 days will be off study treatment.
- Subjects with prolonged renal impairment (CLcr < 70 mL/min) lasting more than 14 days will be off study treatment.
- Subjects who do not demonstrate clinical benefit as per the Investigator at the end of Cycle 4 and beyond will be discontinued from lenalidomide treatment.

